### B.3. INNOVATION

[figure not shown]
This project offers the following two highly innovative features. First, directly comparing PRO effects on impulsivity, as well as smoking cessation and relapse in females and males is highly innovative. Second, chronic use of PRO as a smoking cessation aid has not yet been investigated. Overall, the high level of innovation stems from (a) reliance on previously obtained data from human and animal studies by the experienced study team, (b) the translational strategies of furthering direct comparisons in the proposed clinical and preclinical research, (c) combining extant data to address a unique series of questions regarding determinants and modulators of drug cessation, and (d) use of rigorous multidisciplinary methods (such as thorough neurocognitive assessment of impulsivity, and detailed hormone and menstrual cycle measurement) to implement the projects and answer the questions posed.

### B.4. APPROACH

The two clinical projects - Projects I ([name]) and II ([name]) - will use parallel methods and measures, deviating only as appropriate for the differences in the populations. The details are described below.

#### B.4.1. Study Design

This double-blind, clinical trial (Figure 4) will prescreen an estimated 600 potential subjects, consent and evaluate approximately 300 potential subjects and ultimately enroll 250 subjects to ensure 200 subjects provide a primary relapse outcome measure at four weeks after quit date. Subjects will be stratified by sex then randomized to one of two groups (n=100 per group / 50% female): Progesterone (PRO) or Placebo (PBO). Telephone screening and visit invitation (20 minutes) leads to the consent process and in-person screening including medical-psychiatric evaluation for inclusion/exclusion (two visits, two hours each), then randomization and medication induction (seven days), stable medication (70 days) with medication reduction and final evaluation for secondary outcomes (over the last seven days). These procedures will be conducted as described below.

#### B.4.2. Setting, Recruitment, Subjects

Setting: This project will be conducted at the Delaware Clinical Research Unit (DCRU). The DCRU has both inpatient and outpatient resources for the spectrum of biomedical research including special capabilities that were developed for study of substance use disorders. The Clinical and Translational Sciences Institute (CTSI), runs the DCRU and functions parallel and support the activities of the NIH funded CTSA, which it predated.

The DCRU includes: reception area, examination rooms, meeting rooms, clinical interview rooms, testing rooms for computer based performance tasks, a wet lab for handling bloods and other specimens, freezers (to -80°C), all essential staff offices, each with multiple telephone and computer lines through the University of Minnesota servers, a locked limited access protocol, equipment and medication rooms, as well as secure cabinets for study files and essential supply and support areas and services.

**Recruitment:** To meet recruitment goals, we aim to enroll a total of 250 subjects (~6 subjects/month) to ensure a final sample size of 100 females and 100 males. Our primary recruitment method will be advertising in the mainstream media. While this type of recruitment can be challenging, our team has been successful with this form of recruitment. For example, our current study recruiting females between the ages of 18-40 has had success with Facebook advertising. Specifically, over the past seven months we have advertised on Facebook resulting in 6,483 clicks to our website, an estimated 180 phone calls to our clinic and an enrollment of 29 subjects (~4 subjects/month). We regularly use television, radio, mailings, and other internet sources to identify study subjects with similar success. Using all of these methods, we have successfully enrolled ~8 subjects/month over the past year in our two ongoing tobacco use research studies.

**Subjects and Eligibility:** Females 18-50 years of age with regular menstrual cycles and males, 18-60 years of age, (n=300; 50% females) will be enrolled who are current smokers and are motivated to quit smoking.

**Inclusion Criteria:** • Male 18 to 60 years old or female between 18 and 50 years old; • Self-report smoking ≥ 5 cigarettes/day for at least the past year; • Motivated to quit smoking (self-report ≥ 7 on 10-point Likert-type scale); • In stable physical/mental health; • Self report of regular menstrual cycles (female only) • Willing to use double-barrier contraception method if sexually active and not surgically sterilized; • English fluency; • Understand the study procedures and able to provide informed consent; • Ability to participate fully in research elements for the duration of the trial.

**Exclusion criteria:** • Current use of other types of tobacco, nicotine replacement therapy, or smoking cessation medications; • Current or recent (< 3 months) breastfeeding (females only); • Current or planned pregnancy within the next three months (females only); • DSM-IV diagnoses for psychotic disorders, bipolar disorder, ADHD, major depressive disorder within the last 3 months, • Substance dependence within the last 3 months with the exceptions of nicotine dependence and non-daily use of marijuana.; • Unstable psychotropic medications (< 3 months); • Current use of exogenous hormones, finasteride (propecia), efavirenz, red clover, ketoconazole and other drugs that are CYP3A4 inhibitors; • Conditions contraindicated to progesterone treatment (including, but not limited to, thrombophlebitis, deep vein thrombosis, pulmonary embolus, clotting or bleeding disorders, heart disease, diabetes, history of stroke, allergy to peanuts, hypersensitive to progesterone and liver dysfunction).

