### **Aim 1: Investigate sex differences in the effect of exogenous PRO compared to placebo on impulsivity and smoking cessation**

Hypothesis 1: For both males and females, a lower proportion of subjects randomized to PRO will relapse by 4 weeks after quit date compared to those randomized to PBO.

Hypothesis 2: For both males and females, subjects randomized to PRO will have more days to relapse compared to those randomized to PBO.

Hypothesis 3: There will be a sex difference in smoking relapse such that females, regardless of randomization assignment, will have fewer days to relapse compared to males.

Hypothesis 4: Impulsivity will be a stronger relapse predictor in females than males.

Hypothesis 5: Among those with higher levels of serum PRO the influence of impulsivity on smoking relapse will be dampened.

Given that less than three percent of those who attempt to quit smoking remain abstinent six months later (Benowitz, 2009), there is an urgent need to gain a better understanding of the dynamic process involved in smoking cessation. This project will provide new knowledge regarding the possible protective role of progesterone against smoking relapse in males and females.

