Safety analyses: Adverse events will be quantified separately by sex and treatment groups and compared across treatment groups with Fisher's exact test (for binary events) or with chi-square test (for counts of events or event rates).

Secondary outcome analyses: These address Hypothesis 2. Our secondary outcomes include the binary indicator of relapsed yes/no at the week 12 visit, and days to relapse, as described above. The binary outcome will be analyzed as described for the primary outcome. Days to relapse will be analyzed using Kaplan-Meier

curves with a log-rank test comparing treatments (unadjusted) and Cox proportional hazards analysis (adjusted for other characteristics), both of which allow for loss-to-follow up via right censoring (Therneau and Grambsch, 2000), separately for the CA and PA definitions. Adjusting variables will be selected as described for the primary outcome. The proportional hazards assumption on the treatment effect will be examined and tested (Lin, Wei, and Ying, 1993; Grambsch and Therneau, 1994).

Other analyses: To address Hypothesis 3, we will pool the male and female data and test for an interaction between sex and treatment assignment in an adjusted Cox regression for the days to relapse outcomes. To address Hypothesis 4, we will test a baseline impulsivity by sex interaction in the logistic regressions for the binary outcomes and in the Cox regressions for the days to relapse outcomes. To address Hypothesis 5, we will test a baseline impulsivity by baseline serum progesterone interaction in the logistic regressions for the binary outcomes and in the Cox regressions for the days to relapse outcomes. While this study was designed to be powered for Hypothesis 1, rather than for these comparisons, these will be used to generate preliminary data and hypotheses for future research on sex differences in addiction treatment and impulsivity.

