### Inclusion Criteria

1. Males between 18 and 60 or females between 18 and 50 years of age;
2. Self-reporting smoking  $\geq 5$  cigarettes/day for at least the past year;
3. Motivated to quit smoking (self-report  $\geq 7$  on 10-point Likert-type scale);
4. Stable physical/mental health;
5. Self report of regular menstrual cycles (female only);
6. Willing to use a double-barrier contraception method if sexually active and not surgically sterilized;
7. English fluency;
8. Understanding the study procedures and able to provide informed consent;
9. Ability to participate fully in research elements for the duration of the trial.

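### Men are eligible to 60 but women only to 50, so the pooled sex comparisons for Hypotheses 3 and 4 should also be pre-specified in the shared age range 18-50

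*Combined protocol and SAP*

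**What the plan says.** Section B.4.2 sets the age limits as "Male 18 to 60 years old or female between 18 and 50 years old", and its introductory eligibility sentence gives the same limits. The Data Safety and Monitoring Plan (DSMP) repeats them: "Males between 18 and 60 or females between 18 and 50 years of age". The difference is therefore intended and not a slip. No reason is given for the wider male range, although only women must report regular cycles.

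Aim 1 is to "Investigate sex differences in the effect of exogenous PRO compared to placebo on impulsivity and smoking cessation". Hypothesis 3 states that "females, regardless of randomization assignment, will have fewer days to relapse compared to males". Hypothesis 4 states that "Impulsivity will be a stronger relapse predictor in females than males".

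For Hypothesis 3, the other-analyses paragraph of B.4.8 says "we will pool the male and female data" and then tests a sex-by-treatment interaction in an adjusted Cox model. For Hypothesis 4 it tests a baseline-impulsivity-by-sex interaction in the logistic and Cox models. The Data Analysis Plan in the DSMP repeats both. Neither place restricts these analyses to the shared age range or plans a sensitivity analysis on it.

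Age is the first example in the list of adjusting covariates in B.4.8. The final list was to be settled before first enrolment and is not in the documents. No functional form for age and no interaction involving age is given. Men are matched to women on the delay to the Baseline Visit (B.4.3), not on age.

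**The concern.** Sex is not randomised, so randomisation does not protect a comparison of men with women. If men aged 51-60 differ from younger smokers in relapse risk, or in how strongly impulsivity predicts relapse, some of that difference can be read as a difference between the sexes. No woman of that age is in the trial to show otherwise.

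Three quantities are exposed to different degrees:
- **A sex main effect on days to relapse**, which is what Hypothesis 3 states in words. It is exposed directly to any age effect that the model gets wrong.
- **The sex-by-impulsivity interaction (Hypothesis 4).** It is exposed to an age-by-impulsivity interaction, which an age main effect leaves in place.
- **The sex-by-treatment interaction**, which is the test actually planned for Hypothesis 3. It is exposed only if age modifies the treatment effect, because treatment is randomised within sex.

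At stake is the reading of analyses that the plan intends as a basis for future research on sex differences.

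**Working it through.** **The plan's own figure.** The only design calculation is for the within-sex primary test (B.4.7). With placebo relapse 0.66 and odds ratio 3.5, the progesterone odds are (0.66/0.34)/3.5 = 0.555, so relapse is 0.357. With 50 per arm and two-sided alpha 0.025, power is 79.7% against the stated 80%. It reproduces, and the age limits do not touch it. The documents give no figure for the sex comparisons, so everything below is illustrative.

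**Men without a counterpart.** Assume ages are spread evenly up to each limit. The share of men aged 51-60 is 10/43 = 23.3%, about 23 of 100 completers or 29 of 125 enrolled. Mean ages are (18+60)/2 = 39 and (18+50)/2 = 34, a gap of 5 years.

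**If the age effect is log-linear and the same in both sexes.** Assume a relapse hazard ratio per decade of 0.8 to 1.1. The unadjusted male:female ratio with no true sex effect is 0.8^0.5 = 0.89 to 1.1^0.5 = 1.05. The direction changes within that range. A linear age term removes this bias.

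**If the age effect is not linear.** Assume a hazard 40% lower at ages 51-60 only, no true sex effect, and a linear approximation on the log-hazard scale with 100 men and 100 women. Ages are treated as continuous, 18-61 and 18-51.
- Unadjusted log ratio: 0.2326 × ln 0.6 = -0.119, ratio 0.89.
- Sums of squares and products:
  - sex: 100×100/200 = 50
  - sex with age: 50×5 = 250
  - age: 100×43²/12 + 100×33²/12 + 50×5² = 25,733
  - outcome with sex: 50×(-0.1188) = -5.94
  - outcome with age: 100×(-0.1188)×(56-39.5) + 250×(-0.1188) = -225.7
- Age-adjusted log ratio: (-5.94×25,733 + 250×225.7)/(50×25,733 - 250²) = -0.079, ratio 0.92.

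Linear adjustment removes about a third of the bias (from 0.119 to 0.079). Restriction to 18-50 removes all of it in this scenario, because the assumed effect lies wholly outside that range.

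**Hypothesis 4.** If the impulsivity slope in men aged 51-60 differs by γ from that in everyone else, the average male slope moves by roughly 0.233γ (taking similar impulsivity spread at all ages). The sex-by-impulsivity term takes up that shift. An age main effect does not alter it.

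**Hypothesis 3 as planned.** If the treatment log hazard ratio differs by δ in men aged 51-60, the average male treatment effect moves by roughly 0.233δ. With δ = 0 there is no shift.

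**Cost of restriction.** For a simple contrast, the ratio of standard errors is √[(1/100 + 1/(100(1-s)))/(2/100)], where s is the share of men over 50. It is 1.03, 1.07 and 1.15 for s = 10%, 23% and 40%. For an age-adjusted contrast under even spread, the information on sex is 50 - 250²/25,733 = 47.57 at all ages. In the restricted set it is 76.7×100/176.7 = 43.42. The ratio of standard errors is √(47.57/43.42) = 1.05.

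**The case against.** The strongest reply has four parts.

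- **Age is already provided for.** It is the first covariate named, and the days-to-relapse models choose covariates in the same way. With a common age slope the older men help to estimate that slope, and the 18-50 overlap informs the sex coefficient. This stands against any claim that the model can only extrapolate. What remains is that at ages 51-60 the sex contrast depends on the age form and on there being no age-by-sex interaction, neither of which is specified.
- **The planned Hypothesis 3 test is a sex-by-treatment interaction.** Unadjusted sex ratios do not describe it. This stands. That the test does not address the main effect stated in the hypothesis is a separate matter.
- **The sizes are assumed and small.** An even spread to 60 has no support in the documents, and Section C plans outreach to young adults through campus media and social venues. If 66% of all 200 completers relapsed (an assumption that extends the placebo figure to everyone), there would be 132 events. The standard error of a log sex hazard ratio would be about 2/√132 = 0.17. The residual of 0.079 above is less than half of that. This stands as a limit on importance.
- **The wider male range has a plausible reason, and the analyses are exploratory.** Women need regular cycles and a detected LH surge, and men do not. B.4.8 says the study was not powered for these comparisons. Both points stand. Neither is a reason to leave the shared-range analysis unspecified.

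A reader might also infer that the age limits undo the matching of men to women. They do not: that matching concerns the delay before Baseline and is unaffected.

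**Conclusion.** The point holds in a limited form. Men aged 51-60 can enter the Hypothesis 3 and 4 analyses with no female counterpart. Age adjustment, as far as it is specified, need not deal with this fully. A sex main effect and the Hypothesis 4 interaction are exposed directly, the planned Hypothesis 3 interaction only if age modifies the treatment effect, and Hypotheses 1 and 2 not at all.

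A reader might go further and conclude that the sex comparisons are biased by a known amount, or in favour of the hypothesised direction. The documents do not support that. They give no age distribution and no age-relapse relation, and the sign of the illustrated bias depends on the assumption chosen. The 23% share, the 5-year gap and the 0.89 and 0.92 ratios are illustrations, not estimates. Because these analyses are declared hypothesis-generating, this is a minor improvement and not a flaw in the primary design.

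**What to change.** Leave eligibility, enrolment and the analyses of Hypotheses 1 and 2 unchanged. In the other-analyses paragraph of B.4.8 and the matching text of the DSMP Data Analysis Plan, add that:
- the pooled sex analyses for Hypotheses 3 and 4 are also run in participants aged 18-50, adjusted for age in a stated form, because ages can still differ by sex within that range;
- the Hypothesis 4 models include an age-by-impulsivity term;
- the results are reported beside the all-ages analysis, and a sex difference that appears only in the all-ages version is not attributed to sex.

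Which version leads is a matter of preference. What matters is that both are fixed in advance.

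The cost is wording and one extra set of models. The restricted analysis keeps every woman and drops men over 50. Under even age spread that is about 23% of men and about a 5% larger standard error for an age-adjusted sex contrast. For a simple contrast the increase is 3% to 15% if 10% to 40% of men are over 50.

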#### **B.4.3. Visit Sequence & Procedures**

**Screening Visits (Visits 1 and 2):** Initial screening procedures for Project I and II will be identical except for drug use related criteria, testing and evaluation. Candidates completing the consent process will be screened in a two-visit process. For males, this two-visit process will be scheduled within two weeks of completion of the phone interview. For females, this two-visit process will be completed during the follicular phase of their menstrual cycle to avoid any potential menstrual phase effects on smoking behavior or mood measures, as well as to limit wait time for initial study procedures (details below). Therefore, after the phone screen females will be told to call with the first day of their next period, and then the two-part screening visits will be scheduled during days 1-7 (where Day 1 is the onset of menses) of the menstrual cycle. We have used this procedure with success in our ongoing trial on menstrual phase and depressive symptoms.

At the first of two screening visits (Screening Visit 1), the study will be described in detail to candidates by the study coordinator, and informed consent will be obtained. Subjects agreeing to participate will undergo medical, psychiatric and other evaluation to determine eligibility. The medical evaluation will include: brief physical exam (height, weight, blood pressure, heart rate, and medical history interview), audiotaped psychiatric interview, carbon monoxide level and a blood draw (for measurement of serum hormone levels and liver function via ALT and AST measurement) and a urine pregnancy test (females only). Trained staff will conduct all interviews including the Structured Clinical Interview for DSM-IV (SCID; First, 1995) and instrument administration with audiotapes reviewed regularly to sustain fidelity. Self-report instruments measuring

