impulsivity, personality characteristics, stress, caffeine use, smoking withdrawal and behavior will be completed. At the second screening visit (Screening Visit 2; scheduled within three days of the first screening visit), baseline impulsivity tasks will be completed. Females will then be provided with urine luteinizing hormone (LH) testing kits with instructions for daily use. The quit date will be set based on LH testing results (details below). The investigators will review the data to determine eligibility. Subjects meeting eligibility criteria will be given instructions on when to come back for their Baseline Visit (details below).

**Quit Date Assignment:** This procedure will be identical to Project II and is described in detail here (Table 1). For *female subjects* the quit date will be assigned during the luteal phase. We have selected the luteal phase (typically the last 14 days of the menstrual cycle; Yee et al 1999) for quit date given that our prior work has demonstrated that this menstrual phase is associated with improved smoking cessation outcomes ([name] et al 2008). Therefore, using identical techniques from our prior work ([name] et al 2008) the quit date will be set as follows: First, to determine date of ovulation, female subjects will use LH tests. Several studies by our group and others have shown that ovulation can accurately be predicted by urine LH testing (e.g. [name] et al 1999, [name] et al 2000, [name] et al 2008, Grinsted et al 1989, Luciano et al 1990). Using the First Response urine testing kit (Carter Products), subjects will determine their LH peak with daily urine testing during specific days of the cycle (See Appendix A for instructions). The testing will be done for ten consecutive days starting on Day 8-12 (depending on cycle length). Although the surge may last up to three days, the first day of the surge is most important, because it predicts ovulation 24-48 hours later. In our prior studies, as well as our current study, subjects found the test easy to use and have been compliant. If no LH surge is identified in the first two months, that female subject will be labeled anovulatory and dropped for ineligibility (estimated < 5% occurrence). Second, once ovulation is detected, the baseline appointment and quit date will be scheduled. The baseline appointment will occur within three days of ovulation. Quit date will be set for seven days after the baseline appointment (i.e. seven to ten days after ovulation).

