Since this entails a delay of variable duration from Screening Visit 2 to Baseline

Visit (thus impacting timing of medication initiation) across female subjects, each *male subject* will be matched to a female subject for a similar delay so that, across the male and female groups, study procedures will be follow a similar chronology.

**Baseline Visit (Visit 3):** When the LH surge occurs female subjects will be instructed to come into the clinic within three days for their baseline visit and to start medication. Male subjects will be instructed to come into the clinic according to their assigned delay (per list generated by the Biostatistics Core). This visit will occur seven days prior to quit date. At this visit, subjects will be randomized to PRO or PBO within strata defined by sex. The Statistical Analysis Core (SAC) will generate the randomization tables (one for each sex), and the Clinical Trials Research Pharmacy will use it to determine randomization assignment. Randomization assignment will be stored in a secure file in a secure location at the Clinical Trials Research Pharmacy, to be shared only with the SAC. All other project staff including PI and study coordinator, as well as the participant, will remain blinded to the randomization assignment.

At the baseline visit subjects will provide a blood sample (for hormone assessment), breath sample (to confirm smoking status via carbon monoxide breathalyzer), have their vital signs (blood pressure, heart rate, weight) measured, be informed of their quit date, and receive brief behavioral counseling to prepare for their quit date. At the end of this visit subjects will be paid for their time and given study medication along with instructions for taking the medication (beginning at 8PM that day), as well as a clinic visit schedule for the remaining clinic visits. This visit will take approximately one hour to complete.

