**Table 1. Timing of Study Procedures by Sex**

	Female Subjects	Male Subjects
Initial Phone Interview		Anytime
Screening Visit 1	Menstrual Cycle Days 1-7	Within 2 weeks of Phone Screen
Screening Visit 2		Within 3 days of Screening Visit 1
Baseline Visit	Within 3 days after LH Surge	Delay matched to Female Subject
Medication Start		8PM on day of Baseline Visit
Quit Date		7 days after Baseline Visit
Week 0		Day of Quit Date
Week 1-Week 11		Weekly
Medication End		Day of Week 11 Visit
Final Visit		12 Weeks after Quit Date

Weeks 0-12 (Visits 4-16): The Week 0 clinic visit will occur on the assigned quit date. Subjects will attend clinic visits on a weekly basis thereafter for twelve weeks. At weeks 0-4, week 8 and week 12 blood samples (hormone measurement) will be collected. Urine samples will be collected at all visits from all participants (pregnancy tests for females; and visual inspection of urine color to confirm compliance with taking study medication via riboflavin filler). At weeks 0-4, week 8 and week 12 urine will be saved for biochemical confirmation of smoking status via nicotine/cotinine levels. Subjects will also complete several forms and questionnaires (described below). Subjects will also return the medication bottle and unused medication, be given a new two-week supply and adverse events will be assessed. At Week 11, study medication will be discontinued. Finally, subjects will receive brief smoking cessation behavioral counseling (Appendix A). At the end of each visit subjects will be paid for their time. These visits will take approximately 30-45 minutes to complete.

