A Baseline Visit will occur seven days prior to the subjects assigned quit date. Females will have their assigned quit date set seven to nine days after ovulation. Ovulation will be determined through the use of urine ovulation tests that female subjects will use daily for ten days in a row. Males will have their assigned quit date matched to a female subject for a similar delay and procedure completion. At this visit subjects' weight, blood pressure, heart rate, and carbon monoxide level will be measured. They will also provide urine and blood samples (20cc) for later measurement of nicotine exposure (specifically nicotine and cotinine) and hormone levels (specifically progesterone and estradiol), respectively. At this visit subjects will receive their study medication and be provided regimen/administration instructions. They will also receive brief smoking cessation behavioral counseling, be compensated for their time, and receive a schedule of all follow-up visits.

At the follow-up visits (weekly visits, Week 0 - Week 12) all subjects will have their weight, blood pressure, heart rate and expired carbon monoxide measured. The subjects will provide urine (nicotine, cotinine) at all visits and blood (progesterone, estradiol) samples at visits 0-4, 8 and 12 and complete several forms to measure smoking-related symptomatology, mood, and related items. The study nurse will assess their adverse events. At the end of each visit subjects will receive additional behavioral counseling, additional study medication and be compensated for their time.

Subjects could earn up to \$480 for their study participation (\$25 for screening visit x 2 screening visits + \$20 for baseline visit + \$20 for follow-up clinic visits x 13 visits + \$75 bonus for missing less than three visits + \$75 for completing the study).

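### The planned-pregnancy exclusion has no start date and, counted from screening, often ends before dosing does; no pregnancy test is listed between Screening Visit 1 and the first dose

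*Combined protocol and SAP*

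**What the plan says.** The exclusion criteria in B.4.2, repeated in the DSMP, bar "Current or planned pregnancy within the next three months (females only"). Neither list gives the date from which the three months run. A separate inclusion criterion has no time limit: "Willing to use double-barrier contraception method if sexually active and not surgically sterilized".

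For women, B.4.3 states that "the two-part screening visits will be scheduled during days 1-7 (where Day 1 is the onset of menses"). Screening Visit 1 includes blood tests "and a urine pregnancy test (females only"). The investigators review eligibility after Screening Visit 2, and only eligible women are told when to return for Baseline. The DSMP (Screening and Visit Procedures) likewise makes screening the step that determines final eligibility.

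Baseline then waits for an LH surge, and a second cycle is allowed: "If no LH surge is identified in the first two months, that female subject will be labeled anovulatory and dropped for ineligibility". Randomisation takes place at Baseline and the first dose is taken that evening. Medication lasts twelve weeks, to the Week 11 visit (B.4.5 and Table 1).

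The two descriptions of Baseline differ on urine. B.4.3 says "At the baseline visit subjects will provide a blood sample (for hormone assessment), breath sample" and vital signs, with no urine. The DSMP says "They will also provide urine and blood samples (20cc) for later measurement of nicotine exposure" and hormone levels. Neither mentions a pregnancy test. The next one listed is in the Weeks 0-12 text below Table 1: "Urine samples will be collected at all visits from all participants (pregnancy tests for females").

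**The concern.** An exclusion that looks ahead should cover the period of exposure it is there to prevent. Here the question is put at screening, but exposure starts after a variable wait and then lasts twelve weeks. A woman planning to conceive in the fourth month after screening is not caught by the three-month wording, yet she could still be taking study medication then.

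The second gap concerns current pregnancy. If the wait runs into a second cycle, the only negative test on file may be several weeks old at randomisation. A pregnancy found before randomisation is a screen failure. One found at Week 0 or later is in a randomised woman who has already been dosed. If she then discontinues, the Study Adherence text in B.4.3 classes her as incomplete and does not replace her.

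The stake is mainly participant safety and who is enrolled. The effect on the trial's answer is small.

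**Working it through.** **Inputs from the documents**

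- Screening Visit 1 (SV1): cycle day 1-7 (B.4.3, Table 1).
- LH testing: ten consecutive days from cycle day 8-12 (B.4.3), so a surge can be found from day 8 to day 12 + 9 = day 21.
- Baseline: 0-3 days after the surge (Table 1). The B.4.3 text instead says within three days of ovulation, with ovulation 1-2 days after the surge.
- Baseline to quit date: 7 days. Quit date to last dose (Week 11): 11 x 7 = 77 days.

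**Assumptions.** Three months is 90-92 days. The documents give no cycle length, so 21, 28 and 35 days are shown for a second-cycle surge.

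**Step 1: the plan's own duration.** 7 + 77 = 84 days = 12 weeks, which agrees with B.4.5. B.4.1 gives the same total: 7 + 70 + 7 = 84.

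**Step 2: SV1 to last dose.** Days = (surge day + lag to Baseline) - SV1 day + 84.

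- First-cycle minimum: (8 + 0) - 7 + 84 = 85.
- First-cycle maximum: (21 + 3) - 1 + 84 = 107.
- A second-cycle surge adds one cycle length.
- Using the ovulation wording adds 1 day to the minimum and 2 to the maximum.

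| Surge found in | Table 1 wording (LH) | B.4.3 text (ovulation) |
|---|---|---|
| First cycle | 85-107 | 86-109 |
| Second cycle, 21 days | 106-128 | 107-130 |
| Second cycle, 28 days | 113-135 | 114-137 |
| Second cycle, 35 days | 120-142 | 121-144 |

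A mid-range example: SV1 on day 4 and a surge on day 14 give 14 - 4 + 84 = 94, and up to 97 with a three-day lag. That is 2-7 days beyond three months.

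**Step 3: how often the window falls short.** Any woman whose Baseline is nine or more days after SV1 reaches 9 + 84 = 93 days, past even a 92-day window. For a first-cycle surge there are 7 SV1 days x 14 surge days x 4 lags = 392 combinations. Of these, 293 (75%) exceed 92 days and 340 (87%) exceed 90 days. This weights calendar combinations equally; it is not a forecast of the share of women. Every second-cycle row exceeds 92 days.

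**Step 4: the same count from Baseline.** 84 days lies 6-8 days inside three months. The shortfall therefore depends on the start date, which the criterion omits.

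**Step 5: age of the pregnancy test at first dose.** This is the Step 2 figure minus 84: 1-23 days for a first-cycle surge, 29-51 days for a second-cycle surge with a 28-day cycle, and 36-58 days with a 35-day cycle. The next listed test is at Week 0, which is 7 days after the first dose.

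**Step 6: reach to the primary endpoint.** Week 4 is Baseline + 7 + 28 = Baseline + 35 days. From SV1 that is at most 23 + 35 = 58 days (first cycle), 51 + 35 = 86 (second cycle, 28 days) or 58 + 35 = 93 (second cycle, 35 days). Even counted from SV1, the window reaches Week 4 except for 1-3 days at that last extreme.

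**The case against.** A reader might infer that pregnancy is checked only once in the trial. The documents do not support that: the Weeks 0-12 text provides pregnancy tests at every weekly visit. The gap is confined to the interval between Screening Visit 1 and Week 0.

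A reader might also infer that the exclusion fails to cover dosing altogether. That needs a start date the criterion does not give, and from Baseline the three months cover all 84 days. Some eligibility steps do fall after the first visit: the investigators' review follows Screening Visit 2, anovulatory women are dropped later, and the Rules/Changes sheet checks cigarettes per day at Baseline. What limits this defence is that the DSMP has screening determine final eligibility, and no listed Baseline procedure asks again about pregnancy plans.

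The contraception criterion is a stronger answer. It has no three-month limit, B.4.5 has all women educated on it, and a woman intending to conceive while on medication would have difficulty meeting it. It reduces the number affected but does not mend the wording of the exclusion.

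On the missing test, three points stand. The study-design figure is not available, so the absence rests on the written lists. The phrase about urine at all visits could be read to include Baseline, although it sits in the Weeks 0-12 text. Finally, second-cycle LH testing is counted from a new menses and Baseline follows a detected surge, so a test then could not be expected to show a conception in that same cycle. This last point is an inference, not something the documents state. A Baseline test would help most after a long wait, and only a little even then.

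**Conclusion.** The concern holds in a limited form. The look-ahead has no reference date. If it is applied at Screening Visit 1, it ends before the last dose in most first-cycle schedules, by up to about 15-17 days (107 less 92 or 90). It does so in every second-cycle schedule, by about 21-45 days with a 28-day cycle (113 - 92 to 135 - 90). The 142-day extreme requires an assumed 35-day cycle, and the documents do not say how many women will need a second cycle. Separately, no pregnancy test is listed between Screening Visit 1 and the first dose.

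It would be tempting to conclude that the trial's main result is at risk. The documents do not support this. The window reaches Week 4 in nearly every schedule, Hypothesis 5 is tested with baseline serum progesterone, and sample size, alpha and the primary analysis are unchanged. At most, an occasional randomised woman is lost who could have been a screen failure. This is an inexpensive safety and eligibility correction with a modest gain.

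**What to change.** 1. In B.4.2 and the DSMP exclusion list, state the date from which the look-ahead runs and reconcile it with the 84-day dosing calendar, so that it is tied to the study-medication period. Have it confirmed at Baseline.
2. Reconcile the Baseline Visit text in B.4.3, the Weeks 0-12 text below Table 1 and the DSMP visit description on whether urine is taken at Baseline and what it is used for, so that current pregnancy is checked before randomisation.
3. While editing B.4.3, reconcile the two anchors for the Baseline Visit (LH surge in Table 1, ovulation in the text), which move the calendar by 1-2 days.

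The cost is a short amendment, one urine test per woman and possibly a few more screen failures. The DSMP already has urine collected at Baseline, so if that description is the one kept, no new sample is needed. No statistical section needs to change.
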